## **2.1.5 Safety outcomes**

### **2.1.5.1 Primary safety endpoint**

The primary safety endpoint is the occurrence of a serious adverse events (SAEs) at any time over the 12 month follow-up period. In addition, the number and percentage with an SAE through 28 days of follow-up and through 3 months of follow-up will be summarized (i.e., through one month after prime and booster vaccination).

For the SAEs through 12 months, event counts, overall and by system organ class according to MedDRA®, and percents (with 95% CIs) will be provided by vaccine group. P-values calculated via the Mantel-Haenzel chi-square test with stratification by site will be provided for comparing each vaccine strategy to the pooled placebo. In addition, time to event analyses, e.g., Kaplan-Meier curves and proportional hazards regression, will be carried out for death and for the composite outcome of death or SAE. These analyses will be performed for the full analysis set.

**Note: One participant had an SAE considered related to the vaccine. The great majority of participants received the booster vaccination (see above).**

### **2.1.5.2 Safety listings**

Line listings by vaccine group will be provided for SAEs. Listings will include the vaccine group label, diagnosis, relatedness to vaccine as judged by the medical officer, and time from vaccination (prime and booster) to onset, age, and sex.

### **2.1.5.3 Malaria events**

Malaria events are reported in 3 different ways:

- Malaria is reported as an SAE if the participant was hospitalized due to malaria.
- As part of the hospitalization for an SAE due to a reason other than malaria, a malaria test may be performed and be reported as positive.
- At each follow-up visit, participants are asked about a malaria diagnosis since

the last visit and it is noted whether it was confirmed by a malaria test.

Analyses will be performed for each definition of a malaria event, and of malaria reported as any of these events. Confirmed malaria events will be summarized by vaccine group and compared between vaccine and placebo groups using the Mantel-Haenszel chi-square test with stratification by site.

#### **2.1.5.4 Appendicitis events**

Appendicitis SAE events will be reported separately by site, gender and treatment group.

#### **2.1.5.5 Injection site reactions, targeted symptoms and grade 3 or 4 adverse events at scheduled follow-up visits following prime vaccination**

The number and percentage of participants who report an injection site reaction (any redness or swelling induration) within 30 minutes after prime vaccination (baseline), one week after prime vaccination (day 7), 2 weeks after prime vaccination (day 14), and one month after prime vaccination (day 28) will be summarized. Similarly, the number and percentage of participants who report an injection site reaction 30 minutes after booster vaccination (day 56), one week after booster vaccination (day 63), and one month after booster vaccination (month 3) will be summarized by vaccine group. For these analyses, proportions will be compared between each vaccine strategy and the pooled placebo using the Mantel Haenszel chi-square test stratified by site.

For safety outcomes, comparisons may also be made between each active vaccine and its matching placebo.

Pain/tenderness with activity, itching at injection site, and targeted symptoms are graded as not present or grade 1-4. For each of these, the number and percent of participants with each reported symptom or any of the symptoms will be summarized. For each symptom, the number and percent with each grade will also be summarized. Participants with unsolicited symptoms will be listed. The percent with fever (body temperature > 38.0 °C) will also be summarized. These summaries will be carried at the time points mentioned above. For these analyses, proportions will be compared between each vaccine strategy and the pooled placebo using the Mantel Haenszel chi-square test stratified by site. Comparisons may also be made between each active vaccine and its matching placebo.

**Note: Analyses of safety data after day 56 will be carried out on all participants, including those who did not receive the booster vaccination. As previously noted, a very high percentage of participants received the booster vaccination. Among participant who did not receive the booster, most did not complete questions concerning symptoms at Day 63 and 3 months.**

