In the placebo-controlled regimens, overall frequencies of solicited local and systemic AEs were higher after MVA-BN-Filo and Ad26.ZEBOV, relative to placebo. In addition, there was a trend towards higher overall frequencies of solicited local and solicited systemic events after Ad26.ZEBOV, relative to MVA-BN-Filo. This trend was not observed in the open-label 14-day regimen. The most frequent solicited local AE was injection site pain. The most common solicited systemic AEs were fatigue, headache and myalgia. Grade 3 solicited local AEs occurred in 3 subjects (injection site pain and injection site swelling in 1 subject each, injection site erythema in 2 subjects). These events occurred after Ad26.ZEBOV vaccination. Grade 3 solicited systemic events were also reported in 3 subjects (nausea and headache in 2 subjects each, myalgia and fatigue in 1 subject each). All these events occurred after Ad26.ZEBOV, except fatigue which occurred after placebo. The systemic events after Ad26.ZEBOV were considered to be at least possibly related to vaccination by the investigator. In the open-label regimen, no subjects experienced grade 3 solicited local events. Grade 3 solicited systemic events occurred in 3 subjects after Ad26.ZEBOV (chills and fatigue in 3 subjects each, headache in 2 subjects, pyrexia and nausea in 1 subject each). All were considered to be at least possibly related to vaccination by the investigator. No grade 3 solicited systemic events were reported after MVA-BN-Filo. All solicited (local or systemic) AEs were transient in nature and resolved without sequelae. In the placebo-controlled regimens, the overall frequency of unsolicited AEs was generally comparable between Ad26.ZEBOV, MVA-BN-Filo, and placebo recipients. In the open-label regimen, unsolicited AEs were more common after Ad26.ZEBOV than after MVA-BN-Filo.

Overall, the reported AEs following vaccination were mild in the majority of subjects, transient in nature, and resolving without sequelae. These findings are consistent with the safety profiles observed for similar vaccines. The safety profile of the individual vaccines when used as prime was comparable to that when used as boost.

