### **4.3. TIME PERIOD AND FREQUENCY FOR EVENT ASSESSMENT AND FOLLOW-UP**

#### **4.3.1. Time Period and Frequency Assessment**

##### **4.3.1.1. AE**

Injection site reactions, targeted symptoms of any grade severity, and unsolicited Grade 3 or 4 AEs will be collected and reported on CRFs as defined by the protocol (see [Appendix A](#)). AEs of grade 1 or 2 severity other than injection site reactions and targeted symptoms will not be collected. Grade 3 or 4 signs or symptoms associated with laboratory abnormalities and clinically significant grade 3 and 4 laboratory abnormalities documented by the investigators as AEs should be reported on the CRFs. All other laboratory abnormalities will be summarized using the protocol required laboratory data that is in the central database. Laboratory abnormalities that are considered clinically significant should be reported as AEs or SAEs irrespective of the presence of symptoms.

Sites will be notified of laboratory abnormalities identified as part of the protocol required testing (baseline for all participants and also 7 days after the prime and booster vaccination for children). Laboratory abnormalities will be summarized for each DSMB review. Details for documenting laboratory abnormalities in the participants medical record are provided in the manual of operations.

Injection site reactions will include redness of skin, swelling/induration, pain/tenderness with activity, and itching at injection site.

The targeted symptoms will include reduced activity/somnolence, fatigue, vomiting, chills, abnormal sweating, skin lesions (macules, papules, purpura, petechiae), mouth ulcers, decreased appetite, feverishness, diarrhea, nausea, headache, dizziness, abdominal pain, muscle pain, joint swelling, and joint pain.

For non-verbal children, subjective symptoms may not be assessed and irritability/fussiness, crying, and screaming will be assessed.

Injection site reactions and symptoms will be graded as follows: Grade 1 – symptoms causing no or minimal interference with usual social & functional activities; Grade 2 - symptoms causing greater than minimal interference with usual social & functional activities; Grade 3 - symptoms causing inability to perform usual social & functional activities; and Grade 4 - symptoms causing inability to perform basic self-care functions OR medical or operative intervention indicated to prevent permanent impairment, persistent disability, or death.

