SAEs will be classified by system organ class according to MedDRA®. The total number of events and the number of participants with at least one event will be reported. Mantel-Haenszel chi-square statistics will be used for each pair-wise comparison of the number of participants with an SAE through 12 months of follow-up; time-to-event methods, e.g., Kaplan-Meier, Cox regression, will also be used to compare groups for SAEs over the 12 month follow-up period. Analyses will also be carried out for SAEs judged to be related to the vaccine. If follow-up is extended to 60 months, similar analyses will be performed for SAEs reported through 60 months.

Each vaccine group will be compared with the pooled placebo group using Mantel-Haenszel chi-square tests and time-to-event methods for diagnoses of laboratory-confirmed malaria through 12 months of follow-up.

For safety and efficacy outcomes assessed before the booster at 56 days, the two groups given the rVSVΔG-ZEBOV-GP prime vaccination will be combined for comparisons with pooled placebo group. For outcomes that are assessed after 56 days, each of the three vaccination strategies will be compared with the pooled placebo group.

Mantel-Haenszel chi-square tests will be used to compare each vaccine with placebo for the percent with grade 3 or 4 AEs and with targeted symptoms reported at 7, 14, and 63 days. Similar methods will be used to compare injection site reactions reported immediately following prime vaccination and at 7 and 14 days. Likewise, treatment differences in injection site reactions reported immediately following booster vaccination and through day 63 (7 days after booster vaccination) will be summarized with similar methods. In the event that there is evidence that safety outcomes differ between the two placebo groups, analyses will also be performed for each vaccine versus its matched placebo.

Longitudinal mixed models will be used to compare log-transformed antibody levels collected at multiple follow-up time points during follow-up. Results will be summarized as geometric means and geometric mean ratios. These analyses will be carried out among participants who did not have elevated antibody levels at baseline. Baseline titer level will be included as a covariate. These analyses will be supplemented with scatter plots that display fold increases in antibody titers, line plots, box plots and reverse cumulative distributions of antibody levels at each visit for each vaccine group.

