For children, changes in biochemical and CBC test values after 7 and 63 days will be compared for each vaccine versus the pooled placebo group using analysis of covariance with the baseline laboratory level as a covariate. Laboratory test results will be graded for severity according to the Division of AIDS (DAIDS) AE Table and local laboratory norms, and the proportion with grade 3 or 4 laboratory abnormalities will be compared.

For children, findings based on contacts during the 7 days following the prime and booster vaccination will be summarized each day. Trends over the 7 days will be examined for each vaccine versus placebo comparison.

Subgroup analyses for the primary endpoints and major secondary outcomes, including SAEs and other safety data, will be performed to determine whether vaccine versus placebo differences vary qualitatively across various baseline-defined subgroups. Subgroup analyses will be performed using regression analysis by age, gender, country, vaccination center, health care worker or job involving close contact with EVD cases, baseline laboratory abnormalities, HIV status, and nutritional status as determined by body mass index. An overall test of heterogeneity will provide evidence of whether the magnitude of the vaccine pair-wise comparison for efficacy/safety outcomes varies across these baseline subgroups.

In addition to the separate analysis for adults and children for each vaccine group versus placebo for antibody levels and safety outcomes, the endpoints will also be summarized pooling the data for adults and children. Methods similar to those described above will be used after stratification on age.

Analyses which compare each vaccine group with placebo for immunogenicity and safety outcomes and adjust for age, gender, vaccination center, health care worker or job involving close contact with EVD cases, baseline laboratory abnormalities, HIV status, and nutritional status as determined by body mass index will also be carried out with regression.

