#### **2.1.5.8 Complete blood count and serum chemistries**

Complete blood counts and serum chemistries were measured for children using blood collected at baseline, day 7 and day 63. Laboratory tests were carried out at the vaccination site.

Results will be summarized by vaccine group. At day 7 and day 63 (7 days after the booster vaccination), change from baseline will be summarized by vaccine group, and compared between each active vaccine group and placebo using a linear regression model with vaccine indicators, adjusted for baseline levels. For each vaccine versus placebo comparison, the estimated mean difference, the standard error (SE) of the difference and P-value will be provided. For the analyses using day 7 results, the two rVSV groups will be combined.

All of these analyses will be stratified by site (local site laboratory).

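### The SAP counts only redness or swelling as an injection site reaction, and omits two grade 3–4 comparisons planned in the protocol

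*SAP*

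**What the plan says.** **Injection site reactions.** Protocol 4.3.1.1 states: "Injection site reactions will include redness of skin, swelling/induration, pain/tenderness with activity, and itching at injection site". Protocol 2.4 makes the percent with injection site reactions a secondary objective after both prime and booster. SAP 2.1.5.5 gives the same name to a two-component endpoint, counting those who "report an injection site reaction (any redness or swelling induration) within 30 minutes after prime vaccination (baseline". The next part of that section says "Pain/tenderness with activity, itching at injection site, and targeted symptoms are graded as not present or grade 1-4". It summarizes these items individually and by grade, and compares proportions with pooled placebo by a site-stratified Mantel-Haenszel test. SAP 2.1.6 lists injection site reactions as a subgroup outcome and gives no other definition.

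**Grade 3 or 4 AEs.** Protocol 7.1 plans Mantel-Haenszel tests to "compare each vaccine with placebo for the percent with grade 3 or 4 AEs". The heading of SAP 2.1.5.5 names grade 3 or 4 adverse events, but its only text on unsolicited events is "Participants with unsolicited symptoms will be listed". For children, SAP 2.1.5.6 covers unsolicited grade 3–4 events in the daily diary and adds the number and percent with each event at least once.

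**Laboratory results in children.** Protocol 7.1 plans an analysis of covariance of change from baseline and, after grading by the DAIDS table, says "the proportion with grade 3 or 4 laboratory abnormalities will be compared". In SAP 2.1.5.8, change from baseline is "compared between each active vaccine group and placebo using a linear regression model with vaccine indicators, adjusted for baseline levels". Grading is not mentioned.

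**The concern.** A reader of the final report would take the percent with an injection site reaction to be the endpoint defined in the protocol. As the SAP stands, it would be a narrower quantity under the same name, without pain. In the protocol's account of the first-in-human Ad26/MVA study, "The most frequent solicited local AE was injection site pain". The subgroup analyses would use the same narrower endpoint.

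The second gap concerns severe events. In adults, who have no diary, an unsolicited grade 3 or 4 event that is not an SAE would appear only in a listing, with no percentage and no comparison between arms. The third gap is that graded laboratory abnormalities in children would have no by-arm comparison. The protocol itself describes transient falls in white cells and platelets after rVSV (section 1.1.3, safety profile) and grade 3 neutropenia in two recipients of an Ad26/MVA regimen (section 1.1.2, Phase 1 studies).

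**Working it through.** No sample size, power or alpha figure in the plan bears on this point. The check sets the texts side by side.

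**1. Can the protocol's percentage be recovered from the SAP's tables?** The inputs are the four components in Protocol 4.3.1.1 and the outputs in SAP 2.1.5.5, which are redness-or-swelling, pain, and itching, each as a separate percentage.

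If the component percentages are p1, p2, ..., then max(p) ≤ percent with any ≤ min(100%, sum of p). Where the truth lies depends on how many participants have more than one component, and separate tables do not show that overlap.

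The protocol's own phase 1 summary (section 1.1.2) illustrates this. Among grade 3 local events in the placebo-controlled regimens, pain occurred in 1 subject, swelling in 1 and erythema in 2.
- Lower bound for any event: max(1, 1, 2) = 2 subjects.
- Upper bound: 1 + 1 + 2 = 4 subjects.
- Reported total: 3 subjects, so 4 − 3 = 1 overlap.
- Redness or swelling alone: 2 subjects if the overlap is between redness and swelling, or 3 if it involves pain.

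The component counts give neither the total nor the two-component figure. The counts are too small to estimate anything in this trial.

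**2. Does the SAP's any-symptom summary supply it?** No. The wording in SAP 2.1.5.5 can be read as pooling pain and itching with the systemic targeted symptoms. On that reading it mixes local and systemic events and leaves out redness and swelling. On any other reading it is undefined.

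**3. Grade 3 or 4 AEs.**

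| | Protocol | SAP |
|---|---|---|
| Any grade 3–4 AE, by arm | Mantel-Haenszel test at 7, 14 and 63 days (7.1) | Not specified |
| Unsolicited grade 3–4, scheduled visits | Collected through Day 28 and Month 3 (3.3, 4.3.1.1) | Listed only (2.1.5.5) |
| Unsolicited grade 3–4, children's diary | Week after each dose (3.3, Appendix A) | Number and percent (2.1.5.6) |
| Targeted symptoms, pain, itching by grade | Collected | Summarized and compared (2.1.5.5) |

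The diary covers about 7 of the 28 days after prime (7/28 = 25% of the window) and about 7 of the roughly 35 days from booster to Month 3 (7/35 = 20%). These are shares of time, not of events. Adults (1,401 enrolled, SAP section 2) have no diary.

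**4. Laboratory results.** Protocol 7.1 plans two analyses, change and graded proportions. SAP 2.1.5.8 contains the first only. The laboratory objectives in Protocol 2.4 are worded as changes from baseline, so the SAP meets those objectives but omits the additional planned comparison.

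**5. Is a reason given?** None for any of the three. By contrast, SAP 2.1.4 says openly that participants with elevated baseline antibody are no longer excluded from the primary analysis.

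**The case against.** The strongest reply is that these are authorised changes. Protocol 7.1 says final analyses follow an SAP updated before unblinding, and it introduces its own list as analyses for the DSMB during the trial. SAP section 1 states that it was prepared before unblinding. That stands: the SAP may depart from 7.1. It does not remove the objectives in Protocol 2.4, which still call for the percent with injection site reactions and graded AEs, and it does not explain the departures. A section heading that names grade 3–4 AEs above text that never analyses them suggests an oversight.

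A second reply is that pain and itching are kept and tested, and that the SAP states its narrow definition openly in parentheses. Both are true. Splitting graded items from presence-or-absence items may have been the motive. Neither supplies the composite.

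A reader might go further and infer any of the following, which the documents do not support:
- *The SAP fails to produce the protocol's safety endpoints.* It produces SAEs through 12 months, malaria, fever and individual targeted symptoms, with stratified tests.
- *Severe AEs have no between-arm test.* Severe events that meet the SAE definition are tested under SAP 2.1.5.1, and graded targeted symptoms, pain and itching are compared under 2.1.5.5.
- *Laboratory grades were replaced by mean changes.* The change analysis was already in the protocol. The graded comparison was dropped from beside it.
- *The local reaction rate is understated several-fold, or the change analysis is weak.* Neither document gives rates of pain against redness in this population, or a pattern of laboratory change. Whether a mean or a graded comparison is more sensitive depends on that pattern, so no factor or power figure is offered here.

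**Conclusion.** The point holds within limits. The SAP narrows one secondary safety endpoint from four components to two under an unchanged name. It also leaves out two comparisons planned in Protocol 7.1: the percent with grade 3 or 4 AEs by arm, and the proportion of children with grade 3 or 4 laboratory abnormalities. The AE gap is widest for unsolicited, non-serious events in adults, which are only listed. In children it is partly filled for the week after each dose. No primary endpoint is affected.

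The conclusion rests on the wording of the two documents and on reading the Protocol 2.4 objectives as still in force. The amount by which the reported local reaction rate would fall short of the protocol's cannot be stated: it is zero if everyone with pain or itching also has redness or swelling, and grows with the number who do not. This should be corrected before the tables are produced, but it is not a flaw that threatens the trial.

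**What to change.** 1. In SAP 2.1.5.5, define injection site reaction as in Protocol 4.3.1.1. Report the composite with its four components, and keep it separate from any summary of targeted symptoms. State that SAP 2.1.6 uses the same definition.
2. In SAP 2.1.5.5, add a site-stratified Mantel-Haenszel comparison with pooled placebo of the percent with any grade 3–4 AE, solicited or unsolicited, from prime through Day 28 and from booster through Month 3. Keep the listing. Protocol 7.1 already gives the levels: 0.025 where the two rVSV groups are pooled before the booster, and 0.0167 for three comparisons afterwards.
3. In SAP 2.1.5.8, add the by-arm comparison of DAIDS grade 3–4 laboratory proportions in children at Days 7 and 63, alongside the change analysis.
4. If any of these omissions is intended, say so and give the reason, as SAP 2.1.4 does for baseline antibody.

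The cost is a few paragraphs of SAP text and a few tables. The data are already collected under Protocol 3.3 and 4.3.1.1.
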